5.3. Medical History and Disease History

Medical history will be coded using the MedDRA classification, version 20.0. Medical history will be summarized by system organ class (SOC) and preferred term by treatment group for the ITT and micro-ITT populations. Subjects reporting the same SOC or preferred term more than once will be counted only once for that SOC and preferred term.

The primary site of infection at baseline (pyelonephritis and normal urinary tract anatomy, cUTI with indwelling urinary catheter, urinary retention, neurogenic bladder, partial obstructive uropathy, with azotemia of renal origin or with surgically modified/abnormal urinary tract anatomy, or other diagnosis) will be summarized by treatment group for the micro-ITT, micro-MITT and ME-TOC populations.

Signs and symptoms related to the cUTI (chills rigors, fever, hypothermia, flank pain, pelvic pain, nausea, vomiting, dysuria, urinary frequency, urinary, urgency, cost-vertebral angle

tenderness) will be summarized as none, mild, moderate or severe at baseline by treatment group for the micro-ITT, micro-MITT and ME-TOC populations. Descriptive statistics (mean, SD, median, minimum and maximum value) for baseline temperature (highest daily temperature) will also be presented by treatment group.

5.4. Baseline Microbiology

The microbiological assessment of the baseline blood and urine specimens will be summarized by treatment group for the micro-ITT, micro-MITT and ME-TOC populations. The number and percentage of subjects with a suitable urine specimen obtained, the number of isolates obtained and whether or not the culture was interpretable will be summarized by treatment group. The distribution of the urine collection methods will also be presented.

The pathogenic organisms identified from the baseline blood culture or urine culture specimens will be presented. The number and percentage of subjects with gram-negative organisms (aerobes), overall and within Enterobacteriaceae and non-Enterobacteriaceae, gram-positive organisms (aerobes) and all anaerobes will be presented by genus and species for the micro-ITT, micro-MITT and ME-TOC populations overall and by primary site of infection (pyelonephritis and normal urinary tract anatomy vs. all other diagnoses). The same pathogen identified from both the blood and the urine culture will be counted only once in the summary. The pathogenic organisms identified at baseline from a blood sample will also be presented separately for the micro-ITT population, micro-MITT and ME-TOC populations. The number and percentage of subjects with levofloxacin resistant and ertapenem resistant organisms will also be presented. The number and percentage of subjects with monomicrobial (gram-negative aerobe, gram-positive aerobe, anaerobe) and poly-microbial infections (gram-negative aerobes only, gram-positive aerobes only, anaerobes only, gram-negative aerobe and anaerobe, gram-positive aerobe and anaerobe, gram-negative and gram-positive aerobe, and gram-negative aerobe, gram-positive aerobe and anaerobe) will be provided for specimens from the blood or urine culture.

Several tables providing the frequency distribution of the minimum inhibitory concentrations (MIC) by pathogen as reported by the central laboratory will be provided for the micro-ITT, micro-MITT and ME-TOC populations:

- The MIC distribution to eravacycline of the baseline pathogens.
- The MIC distribution to ertapenem of the baseline pathogens.
- The MIC distribution to levofloxacin of the baseline pathogens.
- The MIC distribution to the study drug received of the baseline pathogens. For those subjects who received the wrong study drug, the summary will be based on actual treatment received.
- MIC summary statistics (ie, range, MIC50 and MIC90) for baseline pathogens to the study drug received. Range will be reported for all pathogens, MIC50 and MIC90 will only be reported for those pathogens with at least 10 isolates in either treatment group.

5.5. Prior and Concomitant Medications

Prior medications will be summarized by WHODRUG (Version March 2016 Format B) Anatomical Therapeutic Chemical Classification (ATC) level 4 (fourth level indicates the chemical/therapeutic/pharmacologic subgroup) and 3 (third level indicates the

therapeutic/pharmacologic subgroup). Medications are considered prior if taken prior to the first dose of study drug or if their start date is unknown. Subjects will be counted only once for an ATC class. Concomitant medications taken during the study treatment period will be similarly summarized. Medications are considered concomitant if taken on or after the first dose of study drug, or if their stop date is unknown or marked as continuing.

The proportion of subjects who receive the following prior and concomitant medications will be summarized by treatment group:

- Systemic antibacterial medications effective in cUTI taken prior to the first dose of study drug (micro-ITT, micro-MITT and ME-TOC populations)
- Systemic antibacterial medications (excluding study drug) taken between first dose of study drug and the TOC visit (micro-ITT, micro-MITT and ME-TOC populations)
- Non-antibacterial medications prior to the first dose of study drug (ITT and Safety populations)
- Non-antibacterial medications taken from the first dose of study drug through the FU visit (Safety population)

5.6. Study Drug Exposure and Compliance

Exposure to study drug (IV and oral) will be characterized by the total duration of treatment (IV and oral), duration of IV treatment, the number of infusion days, the number of active doses (IV only), total IV dose received, the average daily dose over all infusion days, duration of PO treatment, and the number of PO days. Descriptive statistics for each measure of exposure to study drug will be summarized by treatment group for Safety, micro-ITT, and micro-MITT populations.

Duration of treatment is defined as the number of days from when the subject first received study treatment until the day that they last received study treatment and is calculated as (date of last dose – date of first dose +1). Total duration of treatment (IV and PO), Duration of IV treatment and Duration of PO treatment will be calculated separately.

An infusion day is the 24-hour period during which the full daily dose of study drug is to be administered. An infusion day can be coincidental with a calendar day or can start in the afternoon of 1 day and complete in the morning of the next day.

Number of PO days would be calculated as:

$$\text{Number of PO days} = [\text{Duration of PO days} - \text{Number of days dose was missed}]$$

Study drug (IV only) is administered in mg/kg for the eravacycline arm and in g for theertapenem arm. Actual daily dose in mg is dependent on the treatment received, weight (in the case of eravacycline), the volume of drug administered (recorded on the eCRF), and the volume of drug prepared (recorded on the eCRF), as follows:

For eravacycline:

$$\text{actual daily dose (mg)} = 1.5 * \text{weight (kg)} * (\text{total volume of drug administered for dose}) / (\text{total volume of drug prepared for dose})$$

For ertapenem:

actual daily dose (mg) = $1000 * (\text{total volume of drug administered for dose}) / (\text{total volume of drug prepared for dose})$

The average daily dose of eravacycline, expressed as mg and as mg/kg, is based on the dose of active drug per infusion day, as follows:

average daily dose (mg) = $\Sigma \text{actual daily dose (mg) eravacycline over all doses} / \text{number of infusion days}$

average daily dose (mg/kg) = $\text{average daily dose (mg)} / \text{screening weight (kg)}$

It is expected that the average daily dose of eravacycline will be approximately 1.5 mg/kg.

The average daily dose of ertapenem, expressed in mg, is based on the dose of active drug per infusion day, as follows:

average daily dose (mg) = $\Sigma \text{actual daily dose (mg) meropenem over all doses} / \text{number of infusion days}$

The duration of infusions will be listed and deviations from the dosing regimen will be presented.

Treatment compliance will be based on expected doses of study drug (IV and oral) received and will be calculated as the number of doses received/expected number of doses received. The expected number of active doses received is based on the number of days the subject received study drug. A dose is defined as receipt of any amount of study drug received regardless of whether the full volume was infused.

Descriptive statistics of percent compliance as well as the number and percentage of subjects at least 80% compliant will be provided by treatment group for the Safety, micro-ITT, micro-MITT and ME populations.

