Subjects will be randomized and enrolled to one of two treatment arms in a 1:1 ratio: (i) eravacycline or (ii) ertapenem. Eravacycline will be dosed at 1.5 mg/kg IV every 24 hours (q24h) for at least the first 5 doses, and ertapenem will be dosed at 1 g IV q24h for at least the first 5 doses. At a minimum, the first five IV doses must be administered in an in-patient hospital setting; subsequent doses may be administered on an out-patient basis. An IV-to-PO transition can occur after dose 5, provided the subject has demonstrated clinical improvement as defined per protocol (Section 11.3.2). After the EOI, oral study drug (levofloxacin) will be dosed through study drug completion. Subjects requiring more than 5 days of IV dosing will have the days of PO dosing reduced to maintain the maximum number of days on treatment at 10 days IV and PO combined. During PO study drug administration subjects will receive 750 mg of levofloxacin once daily. Subjects with documented allergy to levofloxacin or baseline pathogens from blood or urine cultures that are resistant to levofloxacin may receive an alternate PO antibiotic as described in the Pharmacy Manual. Study drugs will be administered daily according to the dosing schedule in Table 1 below:

Table 1: Study Drug Administration

Treatment Arms	For at least the first 5 doses	After EOI through Study Drug Completion
	IV Infusion	Oral Administration
Eravacycline (IV) / Levofloxacin (PO)	Eravacycline 1.5 mg/kg IV and placebo IV q24h	Levofloxacin 750 mg PO QD
Ertapenem (IV) / Levofloxacin (PO)	Ertapenem 1 g IV and placebo IV q24h	Levofloxacin 750 mg PO QD

Key: EOI = End of IV; IV = intravenous; PO = oral; q24h = every 24 hours; QD = once a day.

Ertapenem dose will be adjusted for subjects with creatinine clearance ≤ 30 mL/min as described in the prescribing information. Levofloxacin dose will be adjusted for subjects with creatinine clearance < 50 mL/min as described in the prescribing information.

Appropriate urine specimens for culture will be collected from a mid-stream urine specimen, a newly-placed urinary catheter, cystoscopy, suprapubic aspiration, or a properly disinfected collection port prior to the start of study drug therapy. These specimens will be cultured and quantified in the local laboratory or a reference regional laboratory. The purified pathogen(s) will be sent to a central microbiology laboratory for confirmation of species identification and

susceptibility testing.

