11.3 Study Drug Administration

11.3.1 Study Drug Administration and Dosing Schedule

Eravacycline and ertapenem when prepared for infusion require different infusion volumes and times. For these reasons, this study has been designed using double-dummy methodology.

Study Drug Infusions:

During each 24-h dose cycle on IV administration days, the subject will receive two infusions. The makeup of the infusions is shown in Table 3 below.

Table 3: Study Drug Infusion Specifications

Infusion Specifications	TREATMENT ARM	
	Eravacycline 1.5 mg/kg IV q24h	Ertapenem 1 g IV q24h
Infusion 1		
final volume (mL) ^a	Weight (kg) x 5 mL/kg	Weight (kg) x 5 mL/kg
drug amount (mg)	Eravacycline Weight (kg) x 1.5 mg/kg	Placebo
conc (mg/mL) ^b	0.3	NA
infusion time (min) ^c	60 ± 10 per IV bag	60 ± 10 per IV bag
Infusion 2		

final volume (mL)	60 mL	60 mL
drug amount (mg)	Placebo	Ertapenem 1 g
conc (mg/mL)	NA	Variable
infusion time (min)	30 ± 10 per IV bag	30 ± 10 per IV bag

^a Final infusion volume per IV bag must not exceed 500 mL; Total infusion volume must not exceed 1000 mL

^b Concentration may be decreased as long as the infusion volume does not exceed 500 mL per IV bag

^c Infusion time may be increased to 120 minutes per IV bag

Key: IV = intravenous; q24h = every 24 hours.

All solutions for infusion will be prepared by an unblinded pharmacist or designee. Specific instructions for preparation of study drugs are included in the Pharmacy Manual for this study.

Ertapenem dose will be adjusted for subjects with creatinine clearance ≤ 30 mL/min in accordance with the approved prescribing information (see Pharmacy Manual). Subjects with creatinine clearance < 50 mL/min at Screening should have their creatinine clearance recalculated at the Day 1-5 visits, and thereafter as clinically indicated, to allow further dose adjustment of study drug as indicated.

The 24-h interval between IV dose cycles can be shortened (but not prolonged) by up to 2-h (i.e., interval of 22-h to 24-h) from the prior dose cycle during dose cycles 1-3 to adapt to a normal hospital schedule. After the 3rd IV dose cycle, the permitted IV administration window is q24h \pm 90 minutes.

At a minimum, the first 5 IV dose cycles must be administered in an in-patient or hospital setting; subsequent doses may be administered on an out-patient basis.

Study Drug Oral Administration:

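### The SAP's ertapenem dose formula uses a fixed 1000 mg and so cannot register a renally adjusted dose that is set when the bag is prepared

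*SAP*

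**What the plan says.** SAP Section 5.6 lists the exposure measures, among them "total IV dose received, the average daily dose over all infusion days", to be summarised by arm in the Safety, micro-ITT and micro-MITT populations. Its stated inputs are these: "Actual daily dose in mg is dependent on the treatment received, weight (in the case of eravacycline), the volume of drug administered" and the volume prepared.

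The eravacycline formula is 1.5 times weight times the volume ratio. The ertapenem formula begins "actual daily dose (mg) = $1000" (the dollar sign is a typesetting remnant) and multiplies that constant by the volume ratio. The daily figures then feed the average: "The average daily dose of ertapenem, expressed in mg, is based on the dose of active drug per infusion day". The formula line beneath that sentence sums "meropenem over all doses", although meropenem is not a drug in this trial.

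Protocol Section 11.3.1 states: "Ertapenem dose will be adjusted for subjects with creatinine clearance ≤ 30 mL/min in accordance with the approved prescribing information". The synopsis (Section 2) has the same rule: "Ertapenem dose will be adjusted for subjects with creatinine clearance ≤ 30 mL/min as described in the prescribing information". Footnote 10 of the protocol's Schedule of Assessments, repeated as footnote 10 of SAP Table 2, allows ertapenem or its placebo to move up or down as creatinine clearance is recalculated.

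**The concern.** The eravacycline formula contains weight, the variable that sets the eravacycline dose. The ertapenem formula contains nothing that reflects a renal adjustment, although both documents provide for one. The volume ratio measures how much of a bag was infused, not how much drug was in it.

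Such subjects are foreseeable. Azotemia of renal origin is a qualifying condition in inclusion criterion 1, and SAP Section 5.2 tabulates baseline creatinine clearance in categories that reach below 15 mL/min. At stake is whether the comparator's total IV dose and average daily dose are reported correctly, and whether those tables can show that the renal adjustment was applied.

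**Working it through.** **Inputs**

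- SAP Section 5.6: dose = 1000 × V_adm / V_prep, where V_adm is volume administered and V_prep is volume prepared.
- Protocol Table 3 (Section 11.3.1): Infusion 2 has a final volume of 60 mL in both arms and contains ertapenem 1 g in the ertapenem arm; its concentration is given as variable.
- Protocol Section 16.2.1: an unblinded pharmacist or designee supplies finished, opaque-covered infusions.
- Not in the documents: the adjusted amount D (mg) and the share q of ertapenem subjects adjusted. Section 11.3.1 refers to the prescribing information and the Pharmacy Manual. Both are varied below as assumptions. The values of D are illustrative and imply nothing about what the dose should be.

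**Step 1. The plan's own figure.** Unadjusted bag, fully infused: 1000 × 60/60 = 1000 mg, which agrees with Table 3. Half infused: 1000 × 30/60 = 500 mg, also correct. The formula works for unadjusted doses.

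**Step 2. Adjusted dose, set at preparation.** The true dose is D × V_adm/V_prep. The ratio of the SAP figure to the true figure is 1000/D, whatever fraction is infused.

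| Assumed D (mg) | SAP, full bag | True | Ratio |
|---|---|---|---|
| 750 | 1000 | 750 | 1.33 |
| 500 | 1000 | 500 | 2.00 |
| 250 | 1000 | 250 | 4.00 |

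**Step 3. Subject adjusted on only some days.** With 2 of 5 infusion days adjusted, the true average is (3 × 1000 + 2 × D)/5, which is 900, 800 or 700 mg for D = 750, 500 or 250. The SAP returns 1000 mg each time.

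**Step 4. Arm mean.** If a share q is adjusted on every IV day and all bags are fully infused, the true mean is 1000(1 − q) + Dq, and the overstatement is 1000 divided by that mean, minus 1.

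| q | D = 750 | D = 500 | D = 250 |
|---|---|---|---|
| 1% | 1000/997.5 − 1 = 0.25% | 1000/995 − 1 = 0.50% | 1000/992.5 − 1 = 0.76% |
| 5% | 1000/987.5 − 1 = 1.27% | 1000/975 − 1 = 2.56% | 1000/962.5 − 1 = 3.90% |
| 10% | 1000/975 − 1 = 2.56% | 1000/950 − 1 = 5.26% | 1000/925 − 1 = 8.11% |

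**Step 5. The alternative practice.** If a 1 g bag were prepared and only part of it infused, the formula would be right: for D = 500, 1000 × 30/60 = 500 mg. Neither document describes this. The fixed 60 mL volume, the variable concentration and the finished bags point to adjustment at preparation.

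**Step 6. What else uses the milligram figure.** Compliance in SAP Section 5.6 counts doses, and any amount received counts as one. The clinically evaluable criteria in SAP Section 3.1.6 use days of study drug and percent compliance. The primary analysis in SAP Section 5.7.1 uses responder counts. None of them uses milligrams.

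**The case against.** A reader might infer that comparator exposure is overstated for every dose-adjusted subject. The documents do not go that far. The inference needs an adjusted dose below 1 g and a reduction made when the bag is prepared, and the details of both lie in the Pharmacy Manual and prescribing information. The first fits 1 g being the only ertapenem amount named. The second fits Table 3 and Section 16.2.1. Both remain inferences. The full factor 1000/D also applies to a subject's average only when every IV day was adjusted, since the dose may change in either direction during treatment.

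A reader might also infer that renal adjustment disappears from the report altogether. That is too strong. Baseline creatinine clearance is tabulated (SAP Section 5.2), individual listings are planned (SAP Section 4.2), and departures from the dosing regimen are to be presented (SAP Section 5.6). Adjusted subjects might be identified from these. None of them corrects the milligram figure, however, and an adjustment that the protocol requires need not count as a departure.

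The size is soft as well: neither D nor q is documented, so the range shows scale only. Finally, the meropenem wording is resolved by its own lead-in sentence and adds nothing to the dose argument.

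What stands is that the formula has no input for the amount prepared, both documents provide for that amount to change, and no other SAP text makes the correction.

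**Conclusion.** The point holds in conditional form as an inconsistency between the SAP's exposure formula and the dose adjustment that both documents describe. If the adjustment is made at preparation and D is below 1 g, ertapenem total IV dose and average daily dose are overstated by 1000/D for the adjusted infusion days. On the assumed ranges this is 1.33 to 4 times for an adjusted dose, and about 0.25% to 8% for the arm mean. If instead a 1 g bag were partly infused, there would be no error.

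The consequence is small. It is confined to two descriptive measures in the exposure tables for three populations. A reader might suspect that the non-inferiority comparison or the evaluable populations are touched; they are not, because neither uses this figure. The correction is worth making because it is specific and cheap. The meropenem reference is clerical.

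**What to change.** In SAP Section 5.6, define the ertapenem actual daily dose as the milligrams of ertapenem prepared for that dose × volume administered / volume prepared. Take the prepared amount from the eCRF if it is captured there. The documents do not show that it is: Protocol Section 11.3.4 mentions dates, times and volumes, and SAP Section 5.6 mentions volumes. If it is not captured, link it from unblinded pharmacy records after database lock, the stage at which SAP Section 2 already brings in the randomization data. In the average daily dose formula, change meropenem to ertapenem.

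The cost is an edit to two formula lines and, possibly, one data linkage. If the prepared milligrams are not held as data, the linkage is the larger part of the work, so availability should be confirmed before the SAP text is finalised. No dose, clinical rule or inferential analysis changes.

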5.7. Efficacy Evaluation

For all efficacy analyses, subjects will be analyzed in the group to which they were randomized. By definition, subjects who receive the wrong study drug are not included in the CE and ME populations. For the primary analysis, subjects who are randomized to the wrong primary site of infection stratum will be analyzed in the stratum to which they were randomized.

5.7.1. Primary Efficacy Analysis

The primary outcome measure is a responder outcome derived from both clinical response and microbiological response at the EOI and the TOC Visit in the micro-ITT population.

Clinical Response:

Clinical response is based on the Investigator Responses on the CRF and is not derived programatically. Clinical response is classified by the Investigator as cure, failure or indeterminate based on the following definitions:

- **Clinical Cure:** Clinical cure is defined as complete resolution or significant improvement of signs and symptoms of the infection such that no rescue/non-study antibacterial therapy is required to treat the cUTI that presented at study entry

- **Clinical Failure:** Subjects are classified as a clinical failure based on:
 - Death related to cUTI at any time point
 - Persistence of clinical symptoms of cUTI or new symptoms have developed
 - Initiation of rescue/non-study antibacterial drug therapy for cUTI
- **Indeterminate/Missing:** If the subject's outcome is neither clinical cure nor clinical failure, then the outcome should be listed as indeterminate/missing, including death where the cUTI is clearly noncontributory. If the Investigator did not complete an assessment or if the subject did not complete the study visit, the outcome is considered missing

Subjects who are assessed as a clinical failure at the EOT visit or beyond will have the failure carried forward to all subsequent visits.

Data for all subjects will be reviewed to ensure the Investigators are following the protocol defined criteria for clinical response and queries will be issued as needed to clarify any response that does not meet the protocol definition.

Microbiologic Response:

Per-subject microbiological response is defined as follows:

- **Microbiological success:**
 - Reduction of the baseline pathogen(s) to $<10^4$ CFU/mL
- **Microbiological failure:**
 - Blood cultures are positive for the baseline pathogen(s), or
 - Urine culture grows $\geq 10^4$ CFU/mL of the baseline pathogen(s)
- **Microbiological Indeterminate/Missing:** No interpretable urine culture data are available

The primary efficacy outcome is defined in [Table 5](#).

Table 5 Primary Efficacy Outcome

Primary Efficacy Outcome		
Clinical Response	Microbiological Response	Responder Outcome
Cure	Success	Responder
Cure	Failure	Non-responder
Cure	Indeterminate / Missing	Indeterminate
Failure	Success	Non-responder
Failure	Failure	Non-responder
Failure	Indeterminate / Missing	Non-responder
Indeterminate / Missing	Success	Indeterminate
Indeterminate / Missing	Failure	Non-responder
Indeterminate / Missing	Indeterminate / Missing	Indeterminate

For the micro-ITT population, the proportion of micro-ITT subjects with a response is defined using the following formula (where the denominator adds to the total number of subjects in the micro-ITT population):

Number of subjects with response

(Number of subjects with a response + Number of subjects with a non-response + Number of subjects with an indeterminate response)

The primary efficacy analyses will be based on the micro-ITT population. The NI test will be a one-sided hypothesis test performed at the 2.5% level of significance. This NI test will be based on the lower limit of the two-sided 95% confidence interval (CI) for both EOI and TOC Visits. The primary efficacy outcome is the percentage of subjects with an outcome of responder (clinical cure and microbiological success) at the EOI and TOC Visits. The primary analysis is unadjusted.

The number and percentage of subjects in each treatment group defined as a responder, non-responder and indeterminate/missing will be tabulated. The null and alternative hypotheses are as follows:

$$H_0: p_1 - p_2 \leq -\Delta \text{ and } H_1: p_1 - p_2 > -\Delta$$

Where p_1 is the responder rate in the eravacycline treatment group, p_2 is the responder rate in the ertapenem treatment group, and Δ is the NI margin of 10%. Note: For H_0 , outcomes at both EOI and TOC visits will be considered. For H_1 , outcomes at EOI or TOC visits will be considered.

To test the null hypothesis, two-sided 95% CIs for the observed difference in responder rates (eravacycline treatment group minus ertapenem treatment group) will be calculated for the micro-ITT population for the EOI and TOC Visits. If the lower limit of both (EOI and TOC Visits) 95% CIs for the difference in responder rates in the micro-ITT analysis set exceeds – 10%, then the null hypothesis will be rejected and the NI of eravacycline to ertapenem will be declared.

The two-sided 95% CIs for NI testing based on the difference of responder rates at the EOI and TOC Visits, will be computed using the method proposed without stratification by Miettinen and Nurminen (Miettinen 1985). For notation purposes, assume 1 represents the eravacycline group (Group 1) and 2 represents the ertapenem group (Group 2).

Based on Miettinen and Nurminen, the 2-sided 95% CI is given by the roots for

$RD = p_1 - p_2$ of the following equation:

$$\chi_{\alpha}^2 = \frac{(\hat{p}_1 - \hat{p}_2 - RD)^2}{V}$$

Where χ_{α}^2 is the cut point of size α from the chi-square distribution ($\chi_{\alpha}^2 = 3.84$ for 2-sided 95% CI), RD is the difference between the 2 true rates ($RD = p_1 - p_2$), \hat{p}_1 is the observed average proportion in the eravacycline group (Group 1), \hat{p}_2 is the observed average proportion in the ertapenem group (Group 2), and

$$V = \left[\frac{\tilde{p}_1(1 - \tilde{p}_1)}{n_1} + \frac{\tilde{p}_2(1 - \tilde{p}_2)}{n_2} \right] \frac{n_1 + n_2}{n_1 + n_2 - 1}$$

Where n_1 is the number of subjects in the eravacycline group (Group 1), n_2 is the number of subjects in the ertapenem group (Group 2), and \tilde{p}_1 and \tilde{p}_2 are the maximum likelihood estimators for the responder rates in the eravacycline and ertapenem groups, respectively, and computed under the constraint that $\tilde{p}_1 - \tilde{p}_2 = RD$.

As stated above, the 2-sided 95% CI for the difference in rates is given by the roots for $RD = p_1 - p_2$ from the equation above, but this equation does not allow for explicit solution for RD . Therefore, a numerical algorithm will be used to obtain the 2 roots (CI) for RD . This CI approach corresponds to the NI test (a p-value approach) proposed by Farrington and Manning.

